# INTRODUCTION

Cataract surgery is one of the most frequently performed surgical procedures and offers significant improvement to the patients' quality of life. For refraction correction at the time of cataract surgery, the range of intraocular lenses available goes from monofocal intraocular lenses to the multifocal ones, including among the options, trifocal and extended depth of focus lenses (EDOF).

Conventional monofocal intraocular lens (IOL) are the most common device implanted¹ due to their low cost, highly predictable distance visual outcome and low incidence of photic symptoms. However, monofocal IOLs have no power to meet the visual expectations for those patients that wish to be less dependent on glasses while performing simple activities brought to us by modern life, like computer work and cell phone usage, since these activities demand an increased need for intermediate or near vision. Trifocal lenses provide the most extended range of vision, and could meet the intermediate and near vision expectations, but also with limitations. Due to their design, these diffractive lenses split the light to distinct foci; as a result, at one focus the indistinct image from the other foci introduces the potential for glare and halos. For some patients, even if they notice this phenomenon, it is not bothersome to the point to complain about it; to others, on the other hand, glare and halos can be so disturbing that they have a very hard time adapting to this new visual reality. Another common complaint is the lower contrast sensitivity, reported by patients with trifocal lenses implanted.

Extended depth of focus, or EDOF, lenses were developed as a bridge to cover the gap between the monofocal and trifocal or multifocal intraocular lenses. EDOF lenses provide spectacle independence for far and intermediate vision and need only a minimal negative defocus for optimized near vision; they are considered the best option for patients aiming to be less spectacle dependent and, at the same time, to avoid some of the side effects and the compromising from trifocal and multifocal IOLs.

Although the performance of EDOF lenses under photopic conditions has been widely investigated, the question about their performance under mesopic conditions remains unanswered.

## 1. OBJECTIVE:

The purpose of this study is to evaluate the visual outcomes of the Symfony lens with OptiBlue and the Vivity lens under mesopic lighting conditions in patients undergoing routine cataract surgery.

### 2. STUDY DESIGN AND METHODS:

## A. Test article:

- Symfony ™OptiBlue®IOL models DXR00V and DXWxxx
- Clareon® Vivity® IOL models CCWET0 and CCWETx
- **A. Study Design:** Prospective, multicenter (up to 2 sites), double masked (subject and evaluator) study.
- **B.** Subjects: A total of 64 subjects who meet the Inclusion/Exclusion criteria will be enrolled.

#### 1. Inclusion Criteria:

Subjects MUST fulfill the following conditions to qualify for enrollment into the trial

- 1. Subject is undergoing bilateral lens extraction with implantation of an EDOF IOL with a target refraction of plano OU.
- 2. Gender: Males and Females.
- 3. Age: 50 years and older.
- 4. Willing and able to provide written informed consent for participation in the study
- 5. Willing and able to comply with scheduled visits and other study procedures.
- 6. Scheduled to undergo standard cataract surgery in both eyes, with 1 to 30 days between surgeries.
- 7. Potential postoperative visual acuity of 0.2 logMAR (20/32 Snellen) or better in both eyes.

#### 2. Exclusion Criteria:

Subjects with ANY of the following conditions on the eligibility exam may NOT be enrolled into the trial.

- 1. Severe preoperative ocular pathology: amblyopia, rubella cataract, proliferative diabetic retinopathy, shallow anterior chamber, macular edema, retinal detachment, aniridia or iris atrophy, uveitis, history of iritis, iris neovascularization, medically uncontrolled glaucoma, microphthalmos or macrophthalmos, optic nerve atrophy, macular degeneration (with anticipated best postoperative visual acuity less than 20/30), advanced glaucomatous damage, etc.
- 2. Uncontrolled diabetes.
- 3. Use of any systemic or topical drug known to interfere with visual performance.
- 4. Contact lens use during the active treatment portion of the trial.
- 5. Any concurrent infectious/non-infectious conjunctivitis, keratitis, or uveitis.
- 6. Clinically significant corneal dystrophy.
- 7. Corneal irregularities potentially affecting visual acuity (i.e., keratoconus, corneal opacities.
- 8. History of chronic intraocular inflammation.
- 9. History of retinal detachment.
- 10. Pseudoexfoliation syndrome or any other condition that has the potential to weaken the zonules.
- 11. Previous intraocular surgery.
- 12. Previous corneal refractive surgery (i.e., LASIK, PRK, RK).
- 13. Subject who declined any type of presbyopia correcting IOL due to concerns with visual disturbances (i.e., halos)
- 14. Previous keratoplasty
- 15. Severe dry eye
- 16. Pupil abnormalities
- 17. Subject who may reasonably be expected to require a secondary surgical intervention at any time during the study (other than YAG capsulotomy, i.e., LASIK)
- 18. Any clinically significant, serious, or severe medical or psychiatric condition that may increase the risk associated with study participation or may interfere with the interpretation of study results.
- 19. Participation in (or current participation) any ophthalmic investigational drug or ophthalmic device trial within the previous 30 days prior to the start date of this trial.

The principal investigator reserves the right to declare a patient ineligible or non-evaluable based on medical evidence that indicates the patient is unsuitable for the trial.

## 3. STUDY PROCEDURES

# A. Informed Consent / Subject enrollment

Potential subjects will be identified from the patients presenting at the clinic. Additionally, a flyer will be placed in the check-in area and an ad will be placed in social media and on the practice website, if deemed necessary. Once identified as a study candidate, the patient will be asked if he/she would like to participate. The subinvestigator, study coordinator or an appropriately trained staff member will answer any and all questions and will obtain informed consent. A copy of the signed informed consent document will be given to the subject. The principal investigator will be available if the subject wants to discuss further details with him. Any testing that is part of the investigative site's standard preoperative cataract evaluation may be performed prior to the informed consent being signed, provided these tests are conducted within 90 days of surgery. The patient will understand that participation in the study, or declining to participate, will not affect his/her quality of care.

No subject will be enrolled into the study that does not meet the inclusion/exclusion criteria and does not sign the current approved informed consent document. Informed consent will be obtained prior to collecting any data for the study. The original signed documents will be maintained by the investigator as a permanent part of the subject's research records.

## B. Surgery Procedures:

Patients will be randomly assigned to one of two groups:

- Group A, bilateral Symfony.
- Group B, bilateral Vivity.

## C. Study Visit Schedule and Assessments (Table 1).

- 1. Visit Schedule: Subjects will be examined at the following intervals:
  - 1. Visit 0: Screening and enrollment: Preoperative evaluation completed not more than eight weeks before surgery
  - 2. Visit 1/1A: Day of Surgery for each eye
  - 3. Visit 2: Month 3: 90 ±15 days postoperative after second eye surgery

### 2. Measurements and evaluations

- 1. Visit 0 (screening): Informed consent process will be conducted during this visit. Assessments include best-corrected distance visual acuity (BCDVA, Snellen chart), manifest refraction, halo and glare simulator, slit lamp examination including dilated fundus exam, cataract density and type, patient satisfaction, visual symptoms and spectacle independence questionnaires, Additionally, patients enrolled at one site (CEP) will have an iTrace done. Any testing that is part of the site's standard of care related to preoperative cataract surgery evaluation may be performed prior to the informed consent being signed, provided these tests are conducted within 90 days of the surgery and notation of the date performed is entered onto the CRF. The surgeon's standard pre cataract surgery treatment will be used in all his patients
- 2. Visit 1/1A (day of surgery for each eye): The surgeon may use his preferred small incision cataract extraction technique (manual phacoemulsification or laser assisted). The lens will be implanted in the capsular bag. The following information will be captured from the day of surgery: phaco technique (manual or laser), lens implanted and power, target refraction for IOL power implanted, additional surgical procedures, intraoperative complications, and any device deficiencies. The surgeon's standard post cataract surgery treatment will be used in all his/her patients.
- 3. Visit 2 (Month 3): Monocular and binocular UCDVA and BCDVA at 4 m, binocular UCIVA and DCIVA (at 66 cm), binocular UCNVA and DCNVA (at 40 cm), binocular BCDVA low contrast (10% and 25%), DC binocular defocus curve, pupil size at 66 and 40 cm will be performed under mesopic conditions (3-5 cd/m²). Additionally, bilateral BCDVA as well as DCIVA and DCNVA will be performed under photopic conditions. Other assessments will include the manifest refraction, I-Trace (at one site only), halo and glare simulator, IOL

orientation (if a toric lens) and dilated fundus exam as deemed necessary by the investigator, patient satisfaction, visual symptoms and spectacle independence questionnaires, and any device deficiencies. A routine slit lamp examination will also be conducted.

All adverse events and complaints will be monitored and recorded at all study visits.

Table 1. Visits and Study Assessments

	Visit 0 Screening	Visit 1/1A DOS	Visit 2 3-Month 90 ±15 days
Informed Consent	X		
Inclusion/Exclusion	X	X	
Demographics/Ocular history	X		
BCVA Snellen	X		
UCVA ETDRS (4m) under mesopic conditions			X*
UCIVA ETDRS (66 cm) under mesopic conditions			X**
UCNVA ETDRS (40 cm) under mesopic conditions			X**
Manifest refraction – Max Plus			X
BCVA ETDRS (4m) under photopic conditions			X**
DCIVA ETDRS (66 cm) under photopic conditions			X**
DCNVA ETDRS (40 cm) under photopic conditions			X**
BCVA ETDRS (4m) under mesopic conditions			X*
BCVA Mesopic low contrast (10%) at 4 m under mesopic conditions			X**
BCVA Mesopic low contrast (25%) at 4 m under mesopic conditions			X**
DCIVA ETDRS (66 cm) under mesopic conditions			X**
DCNVA ETDRS (40 cm) under mesopic conditions			X**
Defocus curve under mesopic conditions			X**

[name], [name] 9

Pupil size at 66 cm under mesopic conditions			Х
Pupil size at 40 cm under mesopic conditions			Х
SLE	X		X
i-Trace‡	X		Х
Halo and glare simulator	X‡‡		X‡‡
Dilated fundus exam	X		χ†
Cataract density / type	X		
Intraoperative data		X	
Toric IOL position		Х	χ†
Questionnaires	X		Х
AE/Device deficiencies		Х	Х

X To be performed as scheduled

- \* Monocular and binocular testing
- \*\* Binocular testing only
- ‡ To be performed at one site only (CEP)
- ‡‡ With and without correction
- †To be performed as deem necessary by the investigator.

DC: distance corrected.

## D. Study endpoint criteria

- 1. Patient Completion of Study: If a study patient has completed the final visit (Visit 5) of the study, he/she is considered to have completed the study.
- 2. Patient Discontinuation: Each study patient may voluntarily discontinue the study at any time they choose. Study patients who cannot complete the study for administrative reasons (e.g., non-compliance, failure to meet visit schedule, etc.) will be discontinued from the study. Study patients discontinued during the enrollment phase (prior to surgery) of the study will be replaced.
- 3. Patient Termination: A study patient will be terminated if the study patient develops any severe adverse event that may be related to the study. A study patient will receive appropriate treatment at the discretion of the investigator. Notification of termination will be clearly documented. These study patients are considered to have completed the study and will not be replaced.

- 4. Study Termination: The investigator with appropriate notification may terminate the study. If, after clinical observations, the investigator feels that it may be unwise to continue the study, he may stop the study.
- 5. Study Completion: The study will be complete when all enrolled patients have completed Visit 5 or have been terminated from the study.

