### C. Study Endpoints

#### 1. Primary Endpoint:

Binocular distance corrected intermediate visual acuity at 66 cm under mesopic conditions.

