# C. Method for Assigning Subjects to Treatment/Dosing Groups N/A

## D. Subject Compliance Monitoring

Since the IOL is implanted at time of cataract surgery, subject compliance will not be an issue in this particular study.

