# E. Packaging, Receiving, Storage, Dispensing and Return $\ensuremath{\mathsf{N}/\mathsf{A}}$

### 7. ETHICAL CONSIDERATIONS

This clinical trial will be conducted in accordance with the principles of the Declaration of Helsinki, and Good clinical practice. The Investigator and all clinical trial staff will conduct the clinical trial in compliance with this protocol. The Investigator will ensure that all personnel involved in the conduct of the clinical trial are qualified to perform their

assigned duties through relevant education, training, and experience. Deviations from the clinical protocol must be documented in each subject's study records including the dates and reasons for each deviation. The PI must ensure that all aspects of the trial follow the applicable regulatory laws and conditions of approval imposed by the IRB.

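### The discontinuation rule gives no route to measure an implanted subject who misses the Month 3 window, so an obtainable primary outcome can be lost

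*Combined protocol and SAP*

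**What the plan says.** All references are to the combined protocol and SAP.

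- **Discontinuation** (Study endpoint criteria, item 2): "Study patients who cannot complete the study for administrative reasons (e.g., non-compliance, failure to meet visit schedule, etc.) will be discontinued from the study". Nothing in the item separates the period before implantation from the period after it.
- **Replacement** (same item): "Study patients discontinued during the enrollment phase (prior to surgery) of the study will be replaced". The item is silent on administrative losses after surgery.
- **Schedule** (Study Visit Schedule and Assessments): "Visit 2: Month 3: 90 ±15 days postoperative after second eye surgery". Table 1 shows no other postoperative examination.
- **Primary endpoint** (Study Endpoints): "Binocular distance corrected intermediate visual acuity at 66 cm under mesopic conditions". Table 1 places it at Visit 2 only, together with every ETDRS acuity, the defocus curve and the postoperative questionnaires.
- **Completion** (Study endpoint criteria, item 1) is tied to a visit that the schedule does not contain: "If a study patient has completed the final visit (Visit 5) of the study".
- **Deviations** (Ethical Considerations): "Deviations from the clinical protocol must be documented in each" subject's records, with dates and reasons.
- **Analysis** (Statistical Analysis): no analysis set, out-of-window rule or missing-data method is given.

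**The concern.** The treatment is a permanent implant. Once both lenses are in, discontinuing a subject for a scheduling failure ends no exposure; it only ends measurement. Because there is a single postoperative assessment, the subject then has no primary value and no earlier postoperative value from which one could be modelled.

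Two things are at stake. One is precision, because the number enrolled equals the number calculated. The other is the integrity of the randomised comparison. People who miss a visit window may do so for reasons connected with how they see or how they recovered, and removing them after randomisation can bias the difference between lenses. The documents give no evidence on how often this would happen or whether it would differ by lens.

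**Working it through.** **1. What a strict reading does to one subject.**

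- The window is 90 − 15 = day 75 to 90 + 15 = day 105 after the second surgery.
- Take a subject with both study lenses who can come only on day 110. This subject has failed to meet the visit schedule, which item 2 names as a reason for discontinuation.
- If the site discontinues, Visit 2 is not done. Table 1 then holds no postoperative acuity for this subject.
- The Visit 5 named in the completion rule offers no later measurement. The schedule consists of Visits 0, 1/1A and 2.

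**2. Reproducing the plan's sample size.** Inputs from the Sample size section: SD 0.122, difference 0.1 logMAR, two-sided alpha 0.05, power 90%, equal groups.

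n per arm = 2 × (1.960 + 1.282)² × (0.122 / 0.1)² = 2 × 10.51 × 1.4884 = 31.3, rounded up to 32.

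This matches the stated 32 per group and 64 in total. The subject total in the Study Design section is also 64, so there is no allowance for loss. The SD is described as that of UCIVA, while the primary endpoint is DCIVA; the figures below carry the protocol's SD over unchanged.

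**3. Power after losses.** Two-sample t-test, noncentral t, with noncentrality 0.1 / (0.122 × √(2/n)) and 2n − 2 degrees of freedom. At n = 32 the noncentrality is 0.1 / (0.122 × 0.25) = 3.28.

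| Evaluable per arm | Power |
|---|---|
| 32 | 89.8% |
| 31 | 88.8% |
| 30 | 87.7% |
| 29 | 86.6% |
| 28 | 85.4% |

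Each subject lost per arm costs about one percentage point. The documents give no rate of missed windows, so the rows are assumed losses, not predictions.

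**4. Size of a possible bias.** As an illustration, assume that all k losses fall in one arm and come at random from its worse half. For a normal outcome, the worse half averages √(2/π) = 0.798 SD from the mean, which is 0.798 × 0.122 = 0.097 logMAR. Removing k of 32 shifts the arm mean by k × 0.097 / (32 − k):

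- k = 1: 0.097 / 31 = 0.003 logMAR
- k = 2: 0.194 / 30 = 0.006 logMAR
- k = 3: 0.291 / 29 = 0.010 logMAR

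Two or three such losses amount to 6% to 10% of the 0.1 logMAR target difference (0.006 / 0.1 and 0.010 / 0.1). The one-sided pattern is an unfavourable assumption.

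**The case against.** The strongest reply is that item 2 covers patients who are unable to complete the study, with a missed schedule given only as an example of why. The completion rule mentions no window, so a subject tested on day 110 could be counted as a completer. This stands in part. A reader might infer that the protocol bars late testing or excludes late data, and it does neither. But a missed schedule is a listed ground, the consequence is mandatory, and no late-visit route is described. With up to two sites, the rule could be applied in two ways.

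Four further inferences are tempting, and the documents do not support them:

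- **That a second eye done more than 30 days after the first falls under the same rule.** The 1 to 30 day interval is an inclusion criterion on how surgery is scheduled. Visit 2 is timed from the second surgery, so a delayed second eye moves the window and does not cause it to be missed.
- **That the protocol contradicts itself by saying "subject compliance will not be an issue in this particular study".** That statement rests on the lens being implanted at surgery. It concerns compliance with treatment, not attendance.
- **That the deviation clause already handles late visits.** It is a general documentation duty. It shows that a late visit could be recorded, not that one is provided for.
- **That replacement after implantation is ruled out.** The plan states replacement for pre-surgery discontinuations and states non-replacement only for adverse-event terminations (item 3). Non-replacement of later administrative losses is the likelier reading, but it is inferred.

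It is also fair to say that a 31-day window may be missed by few subjects, and that differential lateness by lens in a masked trial is conjecture.

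**Conclusion.** The concern holds as a cheap improvement. The stated rule, applied strictly, turns a bilaterally implanted subject who could still be measured into a fully missing one, and nothing else in the plan recovers the value.

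The size is modest: about 2 percentage points of power if two subjects per arm are lost (89.8% to 87.7%) and about 3 if three per arm are lost (to 86.6%). A shift of up to 0.010 logMAR arises if three losses all come from the worse half of one arm. These figures rest on the protocol's SD and difference and on assumed numbers of losses. The case for change rests less on power than on avoiding an exclusion after randomisation that cannot be repaired once the visit has not been done.

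**What to change.** In Study endpoint criteria, item 2, add that for subjects with both study lenses implanted, missing the Visit 2 window is not a reason for discontinuation. Visit 2 is to be performed as soon as possible, and the late date logged as a protocol deviation.

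In Statistical Analysis, state that out-of-window Visit 2 values are included in the primary analysis, and add a sensitivity analysis restricted to visits on day 75 to 105.

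Leave the exits listed under Exclusion Criteria during surgery and the adverse-event termination in item 3 as they are; this change concerns only administrative reasons. In the same amendment, reconcile the final visit named in the completion rules (Visit 5) with the schedule, which ends at Visit 2.

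The cost is a short amendment and one additional analysis. The sample size does not change. The downside is slightly more spread in time since surgery for a few subjects, which the sensitivity analysis addresses.

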#### 3. STATISTICAL CONSIDERATIONS

#### A. Sample size

The sample size estimates depend in large part on the standard deviation (SD) for logMAR UCIVA. Assuming a SD of 0.122 for the two-sided t-test (alpha =0.05) for the intermediate visual acuity endpoint, we will need 32 subjects in each group (Symfony with Optiblue/ Vivity) to detect differences of 0.1 logMAR (1 line difference) with 90% power. Total sample size = 64.

## B. Statistical Analysis

All data will be collected by the site and entered into a database. Subjects will be assigned an ID number. Data analysis will be performed without patient identification. Statistical analysis will be performed using standard descriptive statistics and other tests as deemed appropriate based on the characteristics of the data to be analyzed. All statistical tests will be two-sided and interpreted at a 5% significance level. Comparisons between the groups will be made. Data analysis will be conducted by a third-party consultant.

### C. Study Endpoints

#### 1. Primary Endpoint:

Binocular distance corrected intermediate visual acuity at 66 cm under mesopic conditions.

### 2. Secondary Endpoints:

- a. Defocus curve under mesopic conditions
- b. Binocular low contrast distance visual acuity under mesopic conditions
- c. Uncorrected and distance-corrected near (40 cm) visual acuity under mesopic conditions.
- D. Uncorrected intermediate (66 cm) visual acuity under mesopic conditions

- E. Uncorrected and best-corrected distance (4 m) visual acuity
- F. Non-directed complaints
- G. To evaluate patient's overall satisfaction of their vision
- H. To evaluate patient's spectacle independence
- I. To evaluate visual symptoms using a questionnaire
- J. To evaluate the functional vision questionnaire
- K. Residual mean spherical equivalent refraction
- L. Residual refractive sphere
- M. Residual refractive cylinder
- N. Percentage of eyes with postoperative MRSE accuracy to target ≤ 0.5D

